## **11) Potential benefits to subjects and/or society**

Potential direct benefits to the subjects include knowledge of their personal VOC exposures and reduced exposures to hazardous chemicals in the workplace. As VOCs emitted from small businesses are one of the primary sources of hazardous air pollutants in urban air, particularly in minority neighborhoods, by reducing exposures in these workplaces, we may also reduce neighborhood exposures to these chemicals. This could benefit workers and their families if they live nearby. In our previous work, we have demonstrated that regions of metropolitan Tucson that have the highest levels of hazardous air pollution and emissions from small businesses have higher than expected cases of childhood wheezing illnesses.

## **12) Provisions to protect the privacy of subjects and the confidentiality of data**

- a. Protection of subject privacy:** There will be no personal identifiers (including business name) on any written materials used for exposure assessments, surveys, questionnaires, or other data collection instruments. Businesses will receive an alphanumeric code. During focus groups, participants will be asked to NOT use their names when speaking. We will not discuss or inquire about immigration status at any point during the study. Consent forms and the link between personal identifiers and subject codes will be kept separately from all other study material, in hardcopy form only, within a locked cabinet in Drachman Hall, room A223 at the University of Arizona. All contact information will be kept there until the study is complete. In order to facilitate scheduling of previously consented individuals for air sampling between the three organizations, we will store the link between the participant/business alphanumeric code and identifying information temporarily on UA Box Health, a HIPAA-compliant data storage system, until all visits for the business and its participants are completed (estimated 9 months).
- b. Protection of data confidentiality:** The primary protection against potential risks is a data security plan that includes physical, administrative, and technical aspects for confidentiality and privacy of the data, including personal identifiers. Of particular importance will be the appropriate training of CHWs, interviewers, and program evaluators in maintaining confidentiality and privacy of all data, in addition to their formal training from Collaborative Institutional Training Initiative (CITI). To assure total anonymity of businesses and subjects, alphanumeric codes will be used. Digitized data will be de-identified and stored in a HIPAA-

grade encrypted file storage system (e.g., REDCap). This will include audio recordings of interviews and focus groups, which will be uploaded directly in REDCap. During focus groups, we will ask subjects NOT to use their names. Transcribing of any sort will be completed in a sound-proof room (Medical Research Building, room 113i), with any transcriptions or audio files being uploaded directly into REDCap. Only study personnel as indicated on the VOTF will have access to this information, including audio recordings and transcriptions. Participants are free to withdraw from the study at any time with no penalties. This right will be explained to each participant as part of the informed consent procedure.

These protections should provide confidentiality to the businesses and reduce the risk of economic harm. Ultimately, we anticipate that businesses will participate because they value the health and wellbeing of their workers and would like to reduce their occupational exposures and help them improve their health. Other businesses are likely to self-select out and are not likely to agree to participate in the study.

### **13) Access to Private Information**

- c. **Access to medical records (HIPAA):** N/A – medical records will not be accessed
- d. **Access to educational records (FERPA):** N/A – educational records will not be accessed
- e. **Access to employee records:** N/A – employee records will not be accessed

### **14) Subject compensation**

Subjects in the air monitoring portion of Aim 1 will not be compensated for participation. Subjects in the focus groups portion and interviews of Aim 1 will be paid \$25 cash for their participation.

In Aim 3, owner/managers participating in air sampling will be paid \$10/shift, up to 3 shifts (a total of \$30); owner/managers participating in focus groups will be paid \$15. An owner/manager could be compensated up to \$45 over the course of the study. Employees participating in air sampling will be \$10/shift up to 5 shifts (a total of \$50). An employee can be compensated up to \$50 over the course of the study.

### **15) Medical care and compensation for injury**

No risk of injury is anticipated due to study participation. However, in case of an injury, we do not have any monetary compensation to cover any possible costs related to the injury. Workers will be provided with referral to appropriate community health clinics for follow up if they are concerned about their exposures or any related findings.

### **16) Monitoring for subject safety**

This research does not involve more than minimal risk to subjects. However, because our CHW intervention meets the NIH definition of a clinical trial, we have developed a Data and Safety Monitoring Plan. Data will be monitored by UA investigators not involved in the research, who have substantial experience in human exposure studies. Each data collector will complete a daily log

during the assessment periods, which will include reporting of any breaches of the interviewing process or exposure assessment or any adverse events as well as document instrument calibration. At least two of the following three investigators below will meet to review reports and logs on a quarterly basis to monitor data quality, recruitment, accrual, retention, VOC exposures, and maintaining data security. Data and safety monitoring meetings will be held in a conference room, adjacent to where the hard copies of the data and logs are maintained in locked storage. They will report any data or safety issues immediately to the project investigators and appropriate entities.

The following UA investigators have agreed to provide oversight on data and safety monitoring for this study:

- [name], MS, MPH; Associate Dean of Research, Mel and Enid Zuckerman College of Public Health; Professor, Environmental Health Sciences, Mel and Enid Zuckerman College of Public Health
- [name], DVM, PhD; Interim Department Head and Associate Professor, Pharmacology & Toxicology, College of Pharmacy
- [name], MPH; Professor, Environmental Health Sciences, Mel and Enid Zuckerman College of Public Health

In addition to these protections, project investigators will establish a set of exposure criteria that will be provided to research staff to determine if a workplace presents immediate, severe risk to workers and themselves. Research staff will be trained to call project investigators immediately, and together they will work with the business owners to resolve the issues with the appropriate regulatory and health agencies.

## **17) Withdrawal of subjects**

Subjects may withdraw themselves from the study at any time they wish. Any data collected about chemicals in the air or the subject's views on safety and health in the workplace from focus groups or interviews to that point may be used in this study. The voluntary nature of their participation will be made clear during the consenting process.

Subjects would be withdrawn from the study if it were deemed by any expert on the study team to be in the participant's best interest to withdraw.

## **18) Sharing of results with subjects**

Air monitoring participants will be provided with the results of their exposure assessments and an interpretation of these exposures with respect to activities at the business, as well as any relevant recommendations on how to reduce their exposures. Participants will be referred to appropriate community health clinics for follow up if they are concerned about their exposures.

Owner/managers will be provided the same results materials as given to all air monitoring participants. In doing so, we realize that owner/managers may be able to identify which results correspond to which worker; however, this will be a condition that air monitoring participants will agree to during consenting.

These results will be provided by the CHWs in person, so subjects can ask questions. CHWs will be provided with a list of experts, including the PI and co-investigators, who will be able to provide on-site technical advice to businesses seeking assistance with designing and implementing their control

plans. These experts will be assembled from five UA colleges and include industrial hygienists, engineers, toxicologists, and occupational doctors.

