United States, with a disproportionate burden faced by Latinos. Small businesses pose a particular risk. They are more likely to employ low-wage Latino workers, and often use hazardous solvents containing volatile organic chemicals that can cause asthma, cancer, cardiovascular, and neurological disease; yet their workers lack access to culturally and linguistically appropriate occupational health and pollution prevention information due to economic, physical, and social barriers. CHW-led interventions and outreach in Latino communities have documented increased access to health care and health education and reduced workplace exposures among farmworkers. CHWs are an innovative method to bridge the gap between these small business communities and other stakeholders. The proposed project will capitalize on established partnerships between the University of Arizona, the Sonora Environmental Research Institute, Inc. and the El Rio Community Health Center. A community-engaged research framework will be used to complete three specific aims: 1) Quantify and identify exposures to hazardous chemicals in the two high risk small business sectors common in our target area (i.e., auto repair shops and beauty salons); 2) Work collaboratively with business owners, trade groups, workers and CHWs to design an industrial hygiene-enhanced CHW intervention tailored for each small business sector; and 3) Conduct a cluster randomized trial to evaluate the effectiveness of the CHW intervention at reducing workplace exposures to volatile organic compounds and assess which factors led to successful utilization of exposure control strategies in both male and female-dominated businesses. Businesses will be randomized to either an intervention or delayed intervention group, both of which will receive incentives to participate, such as worksite health screenings. CHWs will work closely with business owners and employees to select and implement exposure-strategies appropriate for their worksite using a menu of complementary strategies of varying complexity and cost. This innovative project has the potential to directly reduce occupational health disparities through a CHW intervention that moves beyond providing occupational health education. The intervention will overcome current barriers by helping marginalized Latino workers and small business owners who may have limited education, literacy, and computer skills to understand the hazards associated with their work, and will empower them to have greater control over their occupational exposures, with the ultimate goal of preventing occupational disease and reducing health disparities.

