## **8) Research procedures involved in the Human Research**

During Aim 3, owner/managers will answer questions about their workplace and practices and complete a survey on ideas about CHW recommendations on reducing exposures (see *Owner\_Consent* document). Owner/managers and employees will have the option to consent into any of the following: wearing an air sampler during their work shift (see *AirSampling\_Consent* document); and/or a survey on health and wellness in the workplace (see *WellnessSurvey\_Consent* document). Owner/managers also have the option to consent to a focus group on ideas about the CHW recommendations on reducing VOC exposures (see *FocusGroup\_Consent* document). Employees will also have the option to consent to answering questions in survey format on ideas about CHW recommendations on reducing VOC exposures (see *PostInterventionQx\_Consent* document).

For the business owner/manager completing the *Owner\_Consent* document, they will be asked questions on: their background and demographics; their workplace and practices so as to help inform the VOC control recommendations; and their ideas about the CHW recommendations on reducing VOC exposures that were recommended in their shop.

For the owner/manager or employee completing the *AirSampling\_Consent* document, they will be asked questions on their background and demographics. Participants of air monitoring will wear a small device called a photo-ionization detector (PID) attached to their clothing during the work shift. The PID can only obtain total VOC exposure levels, and it is not possible to distinguish exposures to individual VOCs if multiple VOCs are present. The PIDs will record at the parts per billion level and will record the total VOC level every 60 seconds. Please see device information included with this submission for more information on the PID. Results of the sampling will be returned to participants individually by a CHW, and then they will be asked a brief survey on how it went to get their results returned to them.

For the owner/manager or employee completing the *WellnessSurvey\_Consent* document, they will be asked questions on their background and demographics and on health and wellness in the workplace. This will take place at the health screening visit.

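### Does returning exposure results with recommendations, with no limit by arm or time, give delayed shops the tested advice too early?

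*Protocol*

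**What the plan says.** Protocol section 18 (Sharing of results with subjects) promises air-monitoring participants their measurements, "an interpretation of these exposures with respect to activities at the business", and "as well as any relevant recommendations on how to reduce their exposures". It continues: "Owner/managers will be provided the same results materials as given to all air monitoring participants", and "These results will be provided by the CHWs in person, so subjects can ask questions". CHWs also hold a list of experts who can offer "on-site technical advice to businesses seeking assistance with designing and implementing their control" plans. The section mentions no Aim, arm, assessment or date.

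Protocol section 8, which describes the Aim 3 procedures, says: "Results of the sampling will be returned to participants individually by a CHW". It does not mention recommendations at that point and gives no timing.

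Protocol section 1 sets out the design: "Businesses will be randomized to either an intervention or delayed intervention group". It describes the intervention this way: "CHWs will work closely with business owners and employees to select and implement exposure-strategies appropriate for their worksite".

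The SAP compares the arms on the change in log total VOC concentration from before to after the intervention. Its mixed model has group, three assessment times and their interaction, fitted separately for auto and beauty shops. It does not say which assessment closes the controlled comparison.

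**The concern.** The tested intervention consists largely of CHW recommendations on lowering exposure. Section 18 describes something close to that: advice on reducing exposure, a face-to-face CHW visit, the same materials for the owner, and access to experts on control plans. Both arms are measured at every assessment. Read literally, a delayed shop measured at baseline could therefore get recommendations along with its baseline results, act on them, and arrive at its control-period assessment with lower exposure.

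The between-arm contrast would then be pulled toward zero as an estimate of the full intervention. It would measure what the intervention adds to report-back with advice. A null result would be hard to read, because it could mean that the intervention failed or that both arms improved on the same advice.

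**Working it through.** **The plan's own figures.** Section 7 of the protocol gives four full-shift measurements in each of three visit periods, and 4 × 3 = 12 per business, as stated. Section 4 gives 120 shops, 60 per sector. The sample size cannot be reproduced, because neither document gives an effect size, standard deviation, intracluster correlation or power.

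**What the texts support, side by side.**

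1. *Who gives the recommendations.* The sentence in section 18 about CHW delivery has results as its subject. That CHWs also give the recommendations is a natural reading, but the sentence does not say it.
2. *Which shops.* Section 18 names no Aim. Aim 1 shops were monitored too, and section 7 bars them from the trial. The concern arises only when section 18 is joined to section 8, and section 8 mentions results alone.
3. *When.* Section 1 randomises shops to intervention or delayed intervention and defines the intervention as help in selecting and implementing exposure controls. Recommendations and control plans are the thing being delayed. A general statement about sharing results does not override that specific allocation rule.
4. *Control plans.* The offer of expert help refers to shops' own control plans. That fits shops already in the intervention best.

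**Two readings and what each implies.** Let f be the fraction of the intervention effect δ that delayed shops gain early. The contrast then estimates (1 − f)δ.

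- *Reading A:* delayed shops get their values and an explanation, and recommendations wait. Recommendations then contribute f = 0. The plan already works, and a timing sentence would only record it.
- *Reading B:* every monitored worker gets recommendations with the results. The randomised comparison is still valid, and (1 − f)δ is the effect over and above report-back.

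**Size under reading B, by assumption only.** With two-sided α = 0.05 (SAP) and an assumed design power, power = Φ[(1 − f)(z₀.₉₇₅ + z_power) − z₀.₉₇₅]. At 80% design power the sum is 1.960 + 0.842 = 2.802. For f = 0.1: 0.9 × 2.802 − 1.960 = 0.56, and Φ(0.56) ≈ 0.71.

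| Assumed f | Power if designed at 80% | Power if designed at 90% |
|---|---|---|
| 0 | 80% | 90% |
| 0.1 | 71% | 83% |
| 0.2 | 61% | 74% |
| 0.3 | 50% | 62% |
| 0.5 | 29% | 37% |

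The documents supply neither f nor the design power, so the table shows sensitivity and is not an estimate.

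**A count that does not measure bias.** With 1:1 allocation assumed, 60 × 1/2 × 4 = 120 delayed-arm shift results per sector could be handed back after one round. At 2:1 to 1:2 allocation the range is 80 to 160. These are results available for report-back. They do not show that any advice was given early or that it changed exposure.

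**The case for a change.** The strongest case for a change is that CHWs meet workers who ask questions, and a field rule should not depend on what the word delayed is taken to imply. No visible text says what a CHW may tell a delayed shop. The SAP does not name the assessment that ends the comparison, so a reader cannot tell which of the two quantities was estimated. Two sentences and a log would settle this cheaply.

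Part of this stands. The timing by arm is not written in the supplied text, and an explicit statement would be clearer. Even under reading A, an interpretation tied to shop activities tells delayed shops something about what raises exposure.

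Three things limit its weight. First, the consent and script for air sampling are listed in section 4 of the application but are not in the public text. Section 18 refers to terms agreed at consent, so the timing may be set out there and its absence cannot be presumed. Second, withholding advice from workers with measured exposures has an ethical cost. Accepting or refusing that cost is for the investigators and the IRB, and it is not a statistical error in either direction. Third, section 2 of the protocol gives a planned end of 08/31/22 and the SAP is dated January 16, 2024. If fieldwork ended as planned, new delivery rules and prospective logging could no longer be applied.

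**Conclusion.** The concern does not call for a change. The documents leave open a route by which delayed shops could receive advice early, but they do not say that this happens, and the delayed-intervention design points the other way. If the team follows the ordinary meaning of that design, the missing sentence is a detail that staff and analysts fill sensibly, and recommendations cause no bias. If the team chose to advise all monitored workers, that is a defensible trade-off. The as-randomised contrast then answers a narrower question, and any dilution from effective advice runs toward no effect, so it would not produce a false claim of benefit.

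The SAP model estimates group-by-time effects at all three assessments, so a between-arm comparison at either later assessment comes from the same fit. Describing when results went back to each arm belongs to ordinary trial reporting.

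This conclusion rests on reading delayed intervention in its usual sense and on the supplied text alone. The size of any dilution cannot be computed from the documents.

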## 19) Future use and long-term storage of data or specimens

Personal information we get from Aim 3 will not be stored for future research. We will use the data (not personal information) from this study for future research.

## 20) Information management

N/A

## 21) Clinical Trials.gov Information

[ClinicalTrials.gov](#) "NCT" number for this trial (provide): NCT03455530

Registration pending

Clinical trial does not require registration (explain):

## 22) Gases

N/A

**SECTION 4: LIST OF ATTACHMENTS FOR THIS SUBMISSION (REQUIRED) (Items listed here are expected to be attached as separate documents. These documents will appear in the UA HSPP IRB approval letter as 'documents submitted concurrently' with the review.)**

Document Name	Version Date
1. Research_Personnel_List_10	1. 10/17/19
2. SiteAuthorization	2. 10/17/19
3. RecruitmentPoster	3. 11/11/19
4. ParticipantInfoForm	4. 10/17/19
5. ParticipantBackgroundDemographics	5. 10/17/19
6. SERI_PreAssessment_SPN	6. 10/17/19
7. SERI_PreAssessment_ENG	7. 10/17/19
8. SERI_Assessment_SPN	8. 10/17/19
9. SERI_Assessment_ENG	9. 10/17/19
10. Site_Authorization_ENG	10. 10/17/19
11. PostInterventionQx_ENG	11. 10/17/19
12. PostInterventionQx_SPN	12. 10/17/19
13. FocusGroup_Questions_ENG	13. 11/11/19
14. FocusGroup_Questions_SPN	14. 11/11/19
15. WellnessSurvey_ENG	15. 10/17/19
16. WellnessSurvey_SPN	16. 10/17/19
17. AirSampling_Consent_ENG	17. 11/11/19
18. AirSampling_Consent_SPN	18. 11/11/19
19. WellnessSurvey_Consent_ENG	19. 10/17/19
20. WellnessSurvey_Consent_SPN	20. 10/17/19

21. FocusGroup_Consent_ENG	21. 11/11/19
22. FocusGroup_Consent_SPN	22. 11/11/19
23. Owner_Consent_ENG	23. 10/17/19
24. Owner_Consent_SPN	24. 10/17/19
25. PostInterventionQx_Consent_ENG	25. 10/17/19
26. PostInterventionQx_Consent_SPN	26. 10/17/19
27. Postcards	27. 10/17/19
28. HealthScreeningFlyer	28. 11/11/19
29. UA_SiteAudit_Auto	29. 10/17/19
30. UA_SiteAudit_Beauty	30. 10/17/19
31. F200	31. 11/11/19
32. AirSampling_Script_ENG	32. 11/11/19
33. AirSampling_Script_SPN	33. 11/11/19
34. FocusGroup_Script_ENG	34. 11/11/19
35. FocusGroup_Script_SPN	35. 11/11/19
36. PostInterventionQx_ENG	36. 11/11/19
37. PostInterventionQx_SPN	37. 11/11/19
38. WellnessSurvey_Script_ENG	38. 11/11/19
39. WellnessSurvey_Script_SPN	39. 11/11/19

### See HSPP website for submission requirements.

#### Items needed for approval:

- Word Versions of Application, Consents, Recruitment and Data Collection
- **F107: Verification of Training Form**
- **Current PI/Co-PI CVs or biosketch**, if not included with copy of grant application
- **Informed Consent/Permission/Assent Form(s)** – including study specific release of information documents, DHHS approved sample consent forms. If consent will not be documented in writing, a script of information to be provided orally to subjects

